Malalignment, such as varus deformities are commonly seen in individuals with knee osteoarthritis. Varus deformity is associated with pain and dysfunctions in individuals with medial knee osteoarthritis. More recently, torsional malalignment is also recognized in knee osteoarthritis. External tibial rotation decreases gradually with the progression of osteoarthritis. Nevertheless, there lacks solid evidence indicate the relationship between torsional alignment

and joint force transmission. Since malalignment plays a vital role in the determination of joint mechanical loading distribution, to clarify the attribution of different components of knee alignment could be beneficial to prognosis evaluation of osteoarthritis progression and function limitation.

The aim of this study is to investigate the inter-relationship between medial knee joint loading, knee alignment and muscle properties. The specific objectives of this study are: (1) to investigate the correlation between hip abduction strength and knee joint loading in individuals with medial knee osteoarthritis; (2) to explore passive tension alteration of superficial heads of quadriceps femoris and its link to joint loading and self-perceived pain; (3) to examine the relationship between knee alignment and joint loading as well as quadriceps passive tension.

Statistical analysis plan

Pearson's r test is used to identify the strength of correlation between the tested parameters. In the analysis of preliminary results, these correlations are assessed by Spearman's rho test. Single regression is used to examine predictability of the two parameters. The difference of parameters between elder with and without knee osteoarthritis is compared by independent t test.

Association between alignment parameters and KAM is assessed by linear multiple regression test.

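### Does using Spearman's rho for preliminary results and Pearson's r otherwise give each correlation two chances at significance, and pain the wrong coefficient?

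*Combined protocol and SAP*

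**What the plan says.** The Statistical analysis plan opens with the main method: "Pearson's r test is used to identify the strength of correlation between the tested parameters". The next sentence reads: "In the analysis of preliminary results, these correlations are assessed by Spearman's rho test". The words pointing back to the first sentence mean that the same pairs of variables are covered by both.

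It then continues: "Single regression is used to examine predictability of the two parameters". An independent t test for the comparison of people with and without knee osteoarthritis follows, and a multiple linear regression for alignment and the knee adduction moment.

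Pain enters through the second objective at the end of the Study Protocol, which is "to explore passive tension alteration of superficial heads of quadriceps femoris and its link to joint loading and self-perceived pain". The pain instrument and its scale are not given, and the plan makes no exception for pain, so Pearson's r is its main method by default.

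The document does not state a significance level, a sample size, the size or purpose of the preliminary analysis, whether its participants re-enter the main analysis, or any rule for choosing between the two coefficients.

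**The concern.** Two coefficients for one set of hypotheses, with no stated precedence, invite three worries.

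- **Repeated testing.** A preliminary test followed by a main test, each at 5%, could give each correlation two chances to be called significant.
- **Different quantities.** Rho measures monotone association and r measures linear association, so preliminary and main figures need not agree. An analyst could favour whichever looks better.
- **Pain.** Self-rated pain is often bounded or ordinal, and rank correlation is commonly preferred for such scales.

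Correlation is the main tool for the study's objectives. If these worries held, they would touch most of its inference.

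**Working it through.** **Inputs.** The document supplies the two methods and the presence of pain as a variable, and no figure to reproduce. Everything else is assumed: two-sided 5% tests; total N of 20, 30, 60 or 100; preliminary participants as a fraction f of 0.3, 0.5, 0.7 or 1.0 of the total, all included in the main analysis.

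**1. Error rate if either result counts.** With two tests at 0.05, the upper bound is 0.05 + 0.05 = 0.10, and under independence the rate is 1 - 0.95² = 0.0975. The two analyses share participants, so the rate was simulated under zero correlation (20,000 replicates per setting). Ranges are over N:

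| f | Normal data | Skewed measure, ordinal pain |
|---|---|---|
| 0.3 | 0.089 to 0.099 | 0.096 to 0.103 |
| 0.5 | 0.085 to 0.090 | 0.089 to 0.096 |
| 0.7 | 0.078 to 0.082 | 0.085 to 0.093 |
| 1.0 | 0.061 to 0.065 | 0.081 to 0.083 |

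**2. Error rate of the main analysis alone.** Pearson's r on all N rejected in 0.046 to 0.054 of replicates across the same settings, including the skewed and ordinal ones. Inflation therefore appears only under the rule that significance in either analysis is a finding, and the plan does not contain that rule.

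**3. How far the coefficients differ.** Under bivariate normality, rho = (6/π) × arcsin(r/2). So r = 0.3 gives 0.288, r = 0.5 gives 0.483 and r = 0.7 gives 0.683, which are gaps of 0.012, 0.017 and 0.017. Skew, outliers or curvature can widen them. The document reports none of these features for its measures.

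**4. Disagreement on significance.** Assume a latent correlation of 0.35 and, where pain is involved, a score rounded and clipped to 0-10. The share of studies in which one test is significant and the other is not:

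| Pair | n = 30 | n = 50 |
|---|---|---|
| Both normal | 12.6% | 10.5% |
| 0-10 pain, normal partner | 11.3% | 10.0% |
| 0-10 pain, lognormal partner, log-SD 0.5 | 14.8% | 14.2% |
| 0-10 pain, lognormal partner, log-SD 0.8 | 19.6% | 19.9% |

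The pain score does not raise disagreement above the all-normal case. Against the normal-partner row, ordinary disagreement between two tests at moderate power accounts for 11.3/14.8 = 76% and 10.0/14.2 = 70% of the figure at log-SD 0.5. At log-SD 0.8 it accounts for 11.3/19.6 = 58% and 10.0/19.9 = 50%. The excess comes from the assumed skew of the other variable.

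**5. Power for pain.** At the same latent correlation:

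- Normal partner: Pearson 0.48 and Spearman 0.43 at n = 30; 0.70 and 0.66 at n = 50.
- Log-SD 0.5: the two tie.
- Log-SD 0.8: Pearson 0.39 and Spearman 0.44 at n = 30; 0.58 and 0.66 at n = 50.

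Neither coefficient is uniformly better for a bounded score.

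**The case for a change.** The strongest case for a change is that the text leaves the matter open. It calls the preliminary assessment a test, gives no reason for switching, and says nothing to stop a preliminary p-value being reported as a finding. A few words would settle it at almost no cost. Simulated disagreement of 15% to 20% under skew also shows that the choice of coefficient can change which correlations are called significant.

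Part of this stands. The reason for the switch and the precedence are not stated, and r and rho are not interchangeable when data are skewed or relations are curved.

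The harm does not follow from the text. The plan gives Pearson as the general method and confines Spearman to preliminary results, so the natural reading is that the main result is Pearson's. A rank method on a small early subset is a plausible reason for the switch, though the plan does not say so. If the single regression is read as simple linear regression, its slope test is the same test as Pearson's, t = r√[(n - 2)/(1 - r²)], so the main methods fit together. The plan attaches no stopping or decision rule to the preliminary results. On pain, the argument for rank correlation needs a scale and a degree of skew that the document does not give.

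**Conclusion.** No change follows. Carried out as written, the plan yields a main Pearson analysis whose false-positive rate is about 5% per correlation, even with skewed or ordinal data in the settings tried. The 6% to 10% rate arises only if preliminary significance is also counted as a finding. That is an assumption, as are the sample sizes, the preliminary fraction, the overlap of participants and the 5% level.

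The missing statement of which analysis is inferential is a gap that an analyst would fill sensibly by resting conclusions on all participants and treating preliminary correlations as descriptive. Writing that down would be tidy but would not alter the analysis.

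Requiring Spearman for pain would be a trade-off. It loses about 4 to 5 percentage points of power with a normal partner and gains about 5 to 8 with a strongly skewed one, and the document does not show which case applies.
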